## Defecation diaries during the follow-up period (weeks 11-12/15-16/19-20/31-32):

Participants will record their bowel movements (BMs), spontaneous defecation or not, complete evacuation or not, degree of straining, and the time, dosage, frequency of rescue medicine or other assistant methods used on the diaries every day of week 11-12/15-16/19-20/31-32. Distribution of the defecation diaries: The diaries of weeks 11-12 will be distributed at the last treatment of week 8. Within week 11, participants will get the diaries of weeks 15-16; within week 15, participants should return the diaries of weeks 11-12, and get the diaries of weeks 19-20; within week 19, participants should return the diaries of weeks 15-16, and get the diaries of weeks 31-32; within one week after week 32, participants should return the diaries of weeks 31-32.

For the participants who do not abide by our treatment protocol strictly, the outcome evaluators should still follow them up through phone, text or a visit to record the related items.

# 2.4.8 Safety Assessment

## 2.4.8.1 Adverse Events

The adverse events are some unintended symptoms, physical signs, or health conditions that show up during the whole trial. They may or may not have causality with the interventions. A health condition or an illness existing before the trial can be deemed as an adverse event (AE) if the situation becomes worse within the study period. An abnormal result of the laboratory examination can be deemed as an AE only if it causes some clinical symptoms and/or require related treatments. We will look for adverse events by asking the participants non-inducing questions at each assessing point. We will also look for the adverse events through participants' self-report, or through physical examination, or by laboratory examination. All the adverse events must be recorded at length on the CRF. If an AE was observed, the following information should be acquired:

- 1. Degree of severity (mild, moderate, severe);
- 2. If it is related to the interventions (affirmably, very likely, possibly, possibly not, affirmably not);
- 3. Duration of the AE (start and end dates, whether still exists at the end of the trial);
- 4. Severe adverse effect (SAE) or not.

SAE is defined as any of the following:

- 1. Fatal or life threatening;
- 2. Permanent or loss of function or disability;
- 3. Need hospitalization or need prolonged hospitalization;
- 4. Severe medical accidents, which need medical or surgical interventions to prevent any of the above occurs.

Solution for controlling the adverse events:

Observation, without any treatment;

Adjusting or stopping the treatment;

Aborting the trial permanently;

Adding combined drugs therapy;

Giving non-pharmacologic therapy;

Hospitalizing or prolonging hospitalization.

All the treatment measures for the adverse events should be recorded in detail on the CRF. We will follow up with the adverse event through the whole trial until its resolution. We will confirm if it is permanent. At every assessing point, we will evaluate the adverse event's severity, relation to our interventions, and arrange appropriate the treatments. The common adverse events related to the interventions are listed in the investigator's brochure. To update the brochure, related adverse events will be announced by the form of investigator's note (IN). We will also discuss with the participants about the adverse events that might occur during the trial.

# 2.4.8.2 Report of the Severe Adverse Events

For participants' safety, from the day they sign the informed consent until 30 days after the end of the study, any SAE no matter if it is related to our interventions or not should be reported to [name] (Project management office, Acupuncture Department, Guang'anmen Hospital of China Academy of Chinese Medical Sciences; [name]) or [name] (Acupuncture Department, Guang'anmen Hospital of China Academy of Chinese Medical Sciences; [name]) within 24 hours. SAE occurs over 30 days after the end of the study is not required to be reported, unless it is related to our interventions. The reoccurrence, complication, or the progression of a reported SAE will be reported as the follow-up information of that SAE within 24 hours. All information of the SAE will be collected and recorded on the form of SAE. Researchers should assess the relation of the SAE with our interventions and fax the finished SAE form to the department of Integrated Medical Safety (IMS) of our project in Guang'anmen Hospital within 24 hours. The SAE form and the fax will be kept together with the CRF in the research center. Acupuncturists and gastroenterologist will make the final decision regarding whether the AEs were TEAEs.

Safety Evaluation:

- 1. Safe, no adverse event, no abnormal examination of the safety index;
- 2. Relatively safe, mild adverse event with no treatment needed, no abnormal examination of the safety index;
- 3. Having safety problems, moderate adverse event which needs relative treatment, mildly abnormal examination of the safety index;
- 4. Withdrawal from the study due to the severe adverse event, or obviously abnormal examination of the safety index.

# 2.4.8.3 Safety and Acceptance Evaluation

The adverse events should be documented in detail over the treatment and follow-up periods. Participants and

acupuncturists will be responsible for recording adverse events.

# Electro-acupuncture Related Adverse Events

Adverse events will be recorded and measured both by participants themselves and acupuncturists. Acupuncturists are responsible for the recording of the EA-related adverse events on the CRF. The adverse events relating to acupuncture include broken needle, nausea during acupuncture, faint caused by needling during the treatment, unbearable pricking (VAS≥7) caused by needling during the treatment, sharp pain lasting more than one hour (VAS≥4) after acupuncture, hematoma or bleeding around the site of needling, numbness or infection around the site of needling, sleeplessness after acupuncture, dizziness after acupuncture, other discomforts (including palpitation, headache, loss of appetite, drowsiness, or aggravation of existing symptoms) after acupuncture. Acupuncturists will record the symptoms, frequency, degree, and the duration of each AE. Pricking caused by needling will be assessed through 10-point visual analog scale (VAS).

### Prucalopride Related Adverse Events

Diarrhea, nausea, abdominal pain, abdominal distention, vomiting, dyspepsia, inappetence, flatulence, abnormal bowel sound, hemoproctia, dizziness, headache, tremor, palpitation, myocardial ischemia/infarction, prolonged QT interval, frequent micturition, fatigue, fever.

## Acceptance evaluation of EA:

We will evaluate the acceptability of acupuncture for the EA group. The acceptability of acupuncture will be evaluated through a point system as following:

- 0= hard to accept;
- 1= a little hard to accept;
- 2= acceptable;
- 3= easy to accept;
- 4= very easy to accept.

The scores of acceptability will be recorded after 5 minutes of the first and tenth treatment (the score will be summed up and divided by 2). If the participant drops out after the first treatment, then the score recorded of the first treatment will be used.

# 2.4.9 Compliance Assessment

The adherence of participants towards treatments were counted via the EA sessions or prucalopride tablets they have received. Prucalopride tablets were recycled back from the participants every two weeks in treatment period and every four weeks in follow-up period, and the number of tablets were documents in CRF by outcome assessors.

[figure not shown]

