# 2.4.4 Blinding

The statisticians, outcome assessors, and data manager who take charge of the diagnosis and differential diagnosis of SCC will be blinded to group allocation. Nurses or postgraduates (outcome assessors) from each site who know nothing about the assignment will be in charge of outcome assessment. And the statistician who knows nothing about assignment from the Institute of Basic Research in Clinical Medicine, China Academy of Chinese Medical Sciences will be responsible for the statistical analyses.

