### 2.4.6.3 Prucalopride Group

Participants will take Prucalopride Succinate (Janssen S.P.A) orally at a dose of 2 mg/day before breakfast for 8 weeks. Participants will undergo an electrocardiogram (ECG) at the 8th week, and the drug will be taken for another 24 weeks if no QT interval elongation or other severe cardiac adverse events (like myocardial infarction, severe arrhythmia, etc.). The use of other medicine for constipation will not be allowed during the trial. Prucalopride will be distributed to the participants beforehand every 2 weeks in the treatment period, and every 4 weeks in the follow-up period. The untaken pills will be recycled on the day of next distribution.

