#### 5.1.3 Blinding

The statisticians, outcome assessors will be blinded to the allocation. Outcome assessors who know nothing about the assignment will take charge of the outcome assessment. And the statistician who knows nothing about assignment from the Institute of Basic Research in Clinical Medicine, China Academy of Chinese Medical Sciences will be responsible for the statistical analysis.

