#### 5. Blinding

The statisticians, outcome assessors, and data managers will be blinded to the allocation. Nurse or postgraduate (outcome assessors) from each site who know nothing about the assignment will take charge of the outcome assessment. And the statistician who knows nothing about assignment from the Institute of Basic Research in Clinical Medicine, China Academy of Chinese Medical Sciences will be responsible for the statistical analysis.

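### Outcome assessors described as blind are also assigned to record prucalopride tablet counts, so the assessor blinding does not hold as written

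*Supplement*

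**What the plan says.** Three places state that the outcome assessors are blind.

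- Final protocol 2.4.4: "Nurses or postgraduates (outcome assessors) from each site who know nothing about the assignment will be in charge of outcome assessment".
- Final protocol 5.1.3: "Outcome assessors who know nothing about the assignment will take charge of the outcome assessment".
- SAP section 5: "The statisticians, outcome assessors, and data managers will be blinded to the allocation".

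The compliance text, worded alike in final protocol 2.4.9 and SAP section 12, measures adherence differently in the two arms: "The adherence of participants towards treatments were counted via the EA sessions or prucalopride tablets they have received". It sets the timetable, "Prucalopride tablets were recycled back from the participants every two weeks in treatment period and every four weeks in follow-up period", and names who makes the record: "and the number of tablets were documents in CRF by outcome assessors".

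The tablets belong to one arm only. Final protocol 2.4.6.3, for the prucalopride group, reads "Participants will take Prucalopride Succinate (Janssen S.P.A) orally at a dose of 2 mg/day before breakfast for 8 weeks". Neither document gives the EA arm a matching placebo.

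**The concern.** The blinding sections and the compliance sections cannot both be followed. A person who enters a prucalopride tablet count for a participant knows that participant's arm.

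Participants and acupuncturists know the treatment by its nature. The only masking the plan claims is that of outcome assessors, statisticians and data managers. If assessor masking is removed by the plan's own procedure, a later report of blinded outcome assessment would describe something the design did not provide. Wherever assessors obtain outcome data themselves, knowledge of the arm could colour how they ask and what they record.

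**Working it through.** The plan gives no figure for this point, so the check sets the relevant sections side by side and adds simple counts.

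**1. Does the record reveal the arm?** Study tablets go only to the prucalopride group (2.4.6.3), and no placebo or double-dummy is described. A tablet count therefore means control, and its continued absence means EA.

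**2. When and how often?** Inputs: an 8-week treatment period and a 24-week follow-up period (2.4.6.5), with tablets returned fortnightly and then four-weekly (2.4.9).

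- Treatment: 8 / 2 = 4 returns, around weeks 2, 4, 6 and 8.
- Follow-up: 24 / 4 = 6 returns, around weeks 12, 16, 20, 24, 28 and 32.
- Total: 4 + 6 = 10.

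These are maxima. Drug beyond week 8 depends on the ECG and cardiac condition in 2.4.6.3, and the sample size allows for 20% dropout. The last return also assumes a closing collection at week 32, because 2.4.6.3 ties returns to the next distribution. The first return falls around the end of week 2, just before the primary window of weeks 3-8.

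**3. How many participants?** 560 planned, allocated 1:1: 560 / 2 = 280 controls are subject to the procedure. The other 280 are identifiable by exclusion.

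**4. By what route could this reach the data?** The final protocol assigns the tasks as follows.

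| Task | Who, according to the text | Section |
|---|---|---|
| Daily diary, source of the primary outcome | Participant | 2.4.7.1, 2.4.7.4 |
| Taking back and verifying diaries | Researchers | 5.3, item 7 |
| Recording adverse events | Participants and acupuncturists | 2.4.8.3 |
| Asking about adverse events | Not specified | 2.4.8.1 |
| Retrieving items from participants who do not follow the protocol | Outcome evaluators | 2.4.7.4 |
| Recording tablet numbers | Outcome assessors | 2.4.9 |

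Only the retrieval row joins the assessor role to the collection of outcome data: "the outcome evaluators should still follow them up through phone, text or a visit to record the related items". I take outcome evaluators and outcome assessors to be the same role. That sentence stands under the follow-up diaries, so its reach into weeks 3-8 is not stated. Section 5.3, item 9, provides for similar contact without limiting the period, but does not name the assessors.

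**5. Is it mended elsewhere?** No section gives the count to separate staff or closes those CRF pages to assessors. The table of major updates concerns only the follow-up windows and the current parameter.

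**The case against.** The strongest reply is that little depends on this blinding. The primary outcome is built from the diary of a participant who knows the arm. Completeness is that person's own sensation, and spontaneous status follows a fixed 24-hour rule. Straining, stool form and PAC-QOL are also self-reported. The main reporting bias is the same whoever logs the tablets. This stands, and it limits the consequence, but it does not reconcile the sections.

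Second, the text says only that assessors document the number. It does not say that they collect or count the tablets, or that one individual both logs tablets and gathers outcomes for the same participant. This also stands. The conflict lies in the role as described, and documenting alone is enough to reveal the arm.

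A reader might go further and infer that assessors who know the arm will influence diary checking and adverse-event recording. The documents do not support that: they give diary verification to researchers, and adverse-event recording to participants and to acupuncturists who know the allocation anyway. A reader might also infer that every control participant is revealed at ten visits. Ten is the ceiling for someone who completes and returns tablets each time; a control participant who never returns tablets might not be revealed this way.

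**Conclusion.** Wrong as written. The latest protocol and SAP both claim an assessor blinding that their own compliance procedure removes. For participants who follow the return procedure, the assessor role learns the arm from about week 2, with up to 4 returns in weeks 1-8 and up to 6 in weeks 9-32; EA is inferred by exclusion.

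The added bias is limited and its size cannot be derived from the documents. The clearest route is retrieval of outcome items, by telephone, message or visit, from participants who do not adhere. It would be too strong to conclude that the primary result is invalid, since that outcome rests on participants who know their treatment in any case.

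The conclusion assumes that no placebo is used, as none is described, and that assessors and evaluators are one role.

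**What to change.** Amend final protocol 2.4.9 and SAP section 12 so that tablet returns and EA session counts are recorded by existing unblinded site staff who take no part in outcome assessment, on CRF pages that outcome assessors cannot open. For tablets, this should be whoever dispenses the drug.

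The treating acupuncturist should not be the tablet recorder. Taking prucalopride for fewer than 180 days excludes a control participant from the per-protocol set (final protocol 7.2, SAP 13.2), and SAP 13.3 uses that set as the sensitivity analysis for the imputed primary outcome. Those records should not be in the hands of the person delivering the competing treatment. For the same reason the count cannot simply be dropped.

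If the task is not moved, final protocol 2.4.4 and 5.1.3 and SAP section 5 should stop describing the outcome assessors as blinded, and the trial report should follow suit.

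The cost is about one sentence in each document, a change in CRF access rights and slight extra work for the dispenser. Treatment, endpoint, sample size and analysis are unchanged. The change removes a built-in unblinding step but does not guarantee masking, since assessors may still speak to participants who know their arm.

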## 3. Flowchart

**FIGURE 2 FLOWCHART** 

#### 5. Quality Control and Quality Guarantee

#### **5.1 Quality Control**

#### **5.1.1 Selection of the Trial Design**

This study adopted a randomized controlled design, which is the most effective measure to avoid the selective bias. This trial adopts the central randomization, which is undertaken by the Chinese Academy of Chinese Medical Sciences. Central randomization with varied blocks can ensure the implement of allocation concealment; therefore, the researchers cannot anticipate the next group. The specific randomization and operation were showed in the handbook.

#### **5.1.2** Restriction of the study subject

Strict inclusion criteria is one important method to control bias. Setting specific inclusion and exclusion criteria makes the study subject strictly limited to a particular range, and reduces the differences between subjects, which is conducive to make objective conclusions on the observed factors.

#### 5.1.3 Blinding

The statisticians, outcome assessors will be blinded to the allocation. Outcome assessors who know nothing about the assignment will take charge of the outcome assessment. And the statistician who knows nothing about assignment from the Institute of Basic Research in Clinical Medicine, China Academy of Chinese Medical Sciences will be responsible for the statistical analysis.

#### **5.1.4 Quality Control Level**

A 3-level monitoring system will be established to periodically assess the performance of the trial: Level 1, Inspection; Level 2, Supervision; Level 3, Audit. Inspection: The investigator of each center will designate at least one researcher who take no part in the intervention manipulation to conduct a quality review of the center; Supervision: for each center, the study organizer (Guang'anmen Hospital, China Academy of Chinese Medical Sciences) will designate at least three researchers who take no part in the intervention manipulation to monitor the quality of the studies of that center; Audit: the Clinical Pharmacological Center of Xuanwu Hospital of Traditional Chinese Medicine will designate at least five quality control personnel to conduct a quality audit of the research.

# **5.2 Quality Guarantee**

Before the start of the clinical trial, we will have a clinical training conference for all the researchers. After the training, the researchers should familiar with the trial protocol, and the standard operation procedure (SOP) of the trial's performance.

### **5.3** Compliance Improvement

The formula of the compliance evaluation is as following:

[figure not shown]
Rate of Compliance=	The times of the treatment accepted by the patient actually	
	The times of the treatment according to the protocol	— ×100%

The rate of compliance no less than 80% will be considered as a good compliance. For getting the rate of compliance no less than 80%, we will take measures as following:

1) Participants will participate the trial of their own accord, and sign the informed consent; 2) Researchers will communicate with the participants frequently, patiently, and with concern for getting a better physician-participant relationship, and explain the related examination, interventions, and form filling at length; 3) Researchers will record the participants' contact information in detail for the convenience of the follow-up; 4) Before the randomization, researchers will inform the participants that all the cost referring to the examination and treatment would be exempted; 5) The defecation diaries of the screening and treatment periods will be distributed weekly; 6) The diaries of the follow-up period will be distributed every 4 weeks; 7) Researchers will take back the completed diaries in time and verify the related items with the participants. We will afford rescue medicines for the participants for severe constipation; 8) We will remind the participants to fill in their defecation diaries in time by affording them brochures, or by texting; 9) For participants who have less compliance, we will still follow them up for recording the related outcomes through phone or message; 10) rescue medicine (bisacridine/glycerin enema) should be provided in time.

#### 6. Data Management

### 6.1 Flowchart of the Data Management

### FIGURE 3 FLOWCHART OF THE DATA MANAGEMENT

#### 6.2 The Raw Data Management and Archiving

We use Remote Data Capture (RDC) system to perform data entry. The research assistants will fill out all the electrical CRF through RDC system. Researchers will inspect the eCRF and signed electrically for the eCRF going into effect. The eCRF and the trace of eCRF revising will be left in the Oracle database.

# **6.3 Data Entry and Storage**

#### 6.3.1 Database Building and Testing, Data Entry Interface

The eCRF will be noted according to the CDISC SDTM standard, and the data entry interface will be generated through the Oracle Clinical software. The data entry interface should be in accordance with the paper-version CRF as far as possible. The inputted data will be stored in the Oracle database. After preliminarily setting up the database, the entry clerks will input some analog data according to the CRF to test the database. The testing contains: (1) the agreement of the data entry interface and the paper-version CRF; (2) the agreement of the exported database and the paper-version CRF.

After the testing, data administrators should revise the database and make a testing report. Then they electrically signed on the approval page of the database to indicate that the testing is completed.

During database testing, the following documents should be stored in the project folder: 1) simulated CRF; 2) annotated CRF and CRF annotation plan; 3) screen capture database entry interface; 4) database test report; 5) database approval signature page.

If the database needs to be updated during the process of the trial, the corresponding document above should also be updated.

# **6.3.2 Data Entry and Inspection**

Research assistants take charge of the data entry for our trial. Before the entry, all the research assistants will accept the related training according to the data entry handbook. Researchers will inspect the database, and then sign electrically to let the data go into effect.

